4.1 GENERAL CONSIDERATIONS

Table 4 Analysis Time Windows

Assessments will be assigned to analysis study days according to visit windows defined below:

Analysis Window Label	Baseline	Day 1	Day 7	Day 14	Day 42	Day 63 (c)	Day 84	
Planned Study Day	1 (a)	1	1	14	42	63	84	
ECGs	ECGs							
Study Day	≤ 1 (a)	1	-	2 to 28	-	-	≥ 71	
Vital Signs,	Vital Signs, KSS							
Study Day	≤ 1 (a)	1	-	2 to 28	29 to 55	-	≥ 71	
Lab (Hematology, Chemistry, Urinalysis)								
Study Day	≤ 1 (a)	-	-	2 to 28 (b)	29 to 55	56 to 70	≥ 71	
ESS								

Study Day	≤ 1	-	-	2 to 28	29 to 70	-	≥ 71			
ESS-CHAD										
Study Day	≤ 1	-	-	2 to 28	29 to 55	56 to 70	≥ 71			
Coagulation	Coagulation									
Study Day	≤ 1 (a)	-	-	-	-	56 to 70	≥ 71			
Vineland-3, RBS-R, CRRI, BAI, PRAS-ASD, SSP, AASP, PedsQL, PROMIS, Anthropometric Measurements										
Study Day	≤ 1 (a)	-	-	-	-	-	≥ 71			
CGI-S, CGI-	l (d)									
Study Day	≤ 1 (a)	-	-	2 to 28 (b)	29 to 70	-	≥ 71			
Neurocogni	itive Battery	/								
Study Day	≤ 1 (a)	1	-	2 to 28 (b)	29 to 70	-	≥ 71			
Sudden Onset of Sleep										
Study Day	≤ 1	-	2 to 10	11 to 28	29 to 55	56 to 70	≥ 71			
(a) Latest assessment prior to intake of first study medication. Use date and time, if available.										

⁽b) May include assessments on day 1 if after the time of first study medication.

If more than one assessment is in the same time window, the assessment that is closest to the planned study day will be selected to enter the summary tables.

Table 5 General Descriptive Statistics

Continuous variables will be summarized with the following descriptive statistics and nomenclature:

n	number of observations or participants
mean	arithmetic mean
SD	standard deviation

⁽c) Planned for adolescent participants only.

⁽d) No baseline for CGI-I.

min	minimum value
q1	first quartile value
median	median value
q 3	third quartile value
max	maximum value

Categorical variables will be summarized and presented with the following nomenclature:

n	frequency
%	percentage

Percentage by category will be based on the number of participants exposed within a category. Categories of NOT REPORTED, MISSING, and/or UNKNOWN will be excluded from summaries if null or n/a.

Besides descriptive summaries, listings, and plots will be provided where deemed necessary. Listings will also include multiple assessments within the same time window.

Table 6 ADaM Datasets

The analysis datasets will be generated in accordance with Clinical Data Interchange Standard Consortium (CDISC) Analysis Data Model (ADaM) Version 2.1. ADaM compliant datasets will be created by the sponsor.

ADaM Dataset Name	Description	Double Programmed ?
ADSL	Subject Level Analysis Dataset	Yes
ADAE	Adverse Events Analysis Dataset	No
ADCM	Concomitant Medications Analysis Dataset	No
ADMH	Medical History Analysis Dataset	No
ADEX	Exposure Analysis Dataset	No

ADVS	Vital Signs Analysis Dataset	Yes
ADEG	ECG Analysis Dataset	Yes
ADLB	Laboratory Analysis Dataset	No
ADDV	Protocol Deviations Analysis Dataset	No
ADSUB	Subcategory Analysis Dataset	Yes
ADCSSRS	C-SSRS Analysis Dataset	No
ADKSS	KSS Analysis Dataset	No
ADVABS3	VABS-III Questionnaire Analysis Dataset	Yes
ADRBSR	RBS-R Questionnaire Analysis Dataset	Yes
ADESS	ESS Questionnaire Analysis Dataset	No
ADSOSQ	Sudden Onset of Sleep Questionnaire Analysis Dataset	No
ADNEURO	Neurocognitive Battery Analysis Dataset	No
ADCRRI	CRRI Questionnaire Analysis Dataset	Yes
ADCGII	CGI-I Analysis Dataset	Yes
ADCGIS	CGI-S Analysis Dataset	No

ADBAI	BAI Analysis Dataset	Yes
ADPRAS	PRAS-ASD Analysis Dataset	Yes
ADSSP	SSP Analysis Dataset	No
ADAASP	AASP Analysis Dataset	No
ADPROMIS	PROMIS Analysis Dataset	No
ADPEDSQL	PedsQL Analysis Dataset	No

4.1.1 Missing Data

Generally, no data imputations will be made.

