- 24 At visits with dosing, the attention tasks of the neurocognitive battery (DET, IDN, and ONB) will be repeated 3-4 hours post dose.
- 25 At visits with dosing, the KSS will be done pre-dose and 3-4 hours post dose.
- 26 At the discretion of the Investigator and Sponsor, participants could be tested for SARS-CoV-2 at screening and at any time during the study.
- 27 Blood chemistry at screening includes estradiol and FSH (both for female participants only).
- 28 TSH, free T4, and HbA1c will be assessed at screening, Week 6, and at the 2-week follow-up.
- 30 Correct version will be predefined on eCOA device: "At baseline" version to be used at pre-baseline and baseline visits; "Since Last Visit" version to be used subsequently.
- 31 Correct version will be predefined on eCOA device: "At baseline" version to be used at screening visit; "Since Last Visit" version to be used subsequently.
- 32 The ability to provide informed consent will be evaluated for each participant by the Principal Investigator using their clinical judgment.
- Hair samples are collected from the study participants who have sufficient hair only (assessed at each collection timepoint). In addition, optional hair samples are collected from the support persons (if consent is given in the applicable Informed Consent Form). All hair strands should be at least 1 cm long.

Table 2 Visit Scheduling Details

Week	Screening	Pre-Baseline	Baseline	Week 1	Week 1	Week 2	Week 6	Week 12	Follow-up (2 Weeks)	Follow-up (6 Weeks)	Early Termination
Day	D-42 to D-15	Day -14	Days -3 to -1	Day 1	Day 7	Day 14	Day 42	Day 84	Week 12 visit + 14 days	Week 12 visit + 42 days	
Visit Window		+/- 3 days			+/- 3 days	+/- 7 days	+/- 7 days	+/- 7 days	+/- 7 days	+/- 7 days	8-day window
On-site assessments	May be split up into two visits within a 7-day window (but up to a 15-day window in case of unexpected delays due to logistical or technical reasons).	May be split into two visits within visit time window.	May be split into two visits within visit time window.	Visit cannot be split.	N/A	Visit cannot be split.	May be split into two visits within visit time window.	May be split into two consecutive days.	May be split into two visits within visit time window.	May be split into two visits within visit time window.	May be split into two visits within visit time window.

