6.7 TREATMENT AFTER THE END OF THE STUDY

The Sponsor does not intend to provide RO7017773 or other study interventions to participants after conclusion of the study or any earlier participant withdrawal.

7. DISCONTINUATION OF STUDY, STUDY TREATMENT AND PARTICIPANT DISCONTINUATION/WITHDRAWAL

An excessive rate of withdrawals (either participants discontinuing study treatment or withdrawing from the study) can render the study non-interpretable. Therefore, unnecessary withdrawal of participants should be avoided and efforts should be taken to

motivate participants to comply with all the study-specific procedures as outlined in this protocol.

Details on study and site closures are provided in Appendix 1 Study Governance Considerations Study.

7.1 **DISCONTINUATION OF STUDY TREATMENT**

For data to be collected at the time of treatment discontinuation and follow-up and for any further evaluations that need to be completed, see the SoA (Section 1.3).

Reasons for discontinuation of study treatment (or withdrawal from the study) may include but are not limited to the following:

- Participant unable to continue to comply with the study treatment and study requirements
- Any medical condition that the Investigator or Sponsor determines may jeopardize the participant's safety if he or she continues in the study
- Investigator or Sponsor determination that treatment discontinuation is in the best interest of the participant
- Pregnancy
- Any event that meets the stopping criteria defined in Section 4.1.2
- Specific adverse events if discontinuation of treatment is required to manage the event

Every effort should be made to obtain information on participants who withdraw from the study treatment but have not withdrawn consent. Participants who discontinue study treatment prematurely will be asked to return to the clinic for a study completion/early termination visit and may undergo follow-up assessments (see Section 8.11.3), unless the participant withdrew consent. The primary reason for premature study treatment discontinuation should be documented on the appropriate eCRF. Participants who discontinue study treatment prematurely will not be replaced.

7.1.1 **Temporary Interruption**

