8.11.3 Assessments at Follow Up /Early Termination Visit

Participants who complete the 12-week study treatment period will be asked to return to the clinic approximately 2 weeks and 6 weeks after the last dose of study treatment for safety follow-up visits (see Section 1.3).

Assessments at the follow-up/early termination visits will be performed as indicated in the SoA (see Section 1.3). After the study completion/early termination visit, AEs should be followed as outlined in Sections 8.3.1 and 8.3.3.

If participants discontinue from the study early (as described in Section 4.1.2 and Section 7), all efforts should be made to ask participants to return to the clinic for an early termination visit. All AEs should be followed up until they are resolved and additional unscheduled safety assessments should be performed at Investigator's discretion after discussion with the Medical Monitor if required.

8.11.4 **Assessments at Unscheduled Visits**

Unscheduled visits will be performed for safety reasons (e.g., for repetition of safety laboratory sampling). If due to a safety-related event a participant is unable to physically go to the site for an unscheduled visit, blood and urine samples may be collected by the home nurse services.

The unscheduled visit should be used to collect all assessments that are missing at that time.

If a COA (see Section 8.1.5) cannot be completed during the visit or for a scale, the total score (e.g., the composite scores for Vineland™-3) cannot be calculated with the available data, the scale should be repeated via the phone within the corresponding visit window or at an unscheduled visit as soon as possible (within the next 7 days).

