Appendix 4 Clinical Laboratory Tests

The tests detailed in Table 1 will be performed by the central laboratory. If the local laboratory results are used, the results must be captured in source documentation and entered into the eCRF.

Local laboratory results are only required for the serum and urine pregnancy test and in the event that the central laboratory results are not available in time for either study treatment administration and/or response evaluation. If a local sample is required, it is important that the sample for central analysis is obtained at the same time. Additionally, if the local laboratory results are used to make either a study treatment decision or response evaluation, the results must be captured in source documentation and entered as a comment into the eCRF}.

Protocol-specific requirements for inclusion or exclusion of participants are detailed in Sections 5.1 and 5.2, respectively, of the protocol.

Additional tests may be performed at any time during the study as determined necessary by the Investigator or required by local regulations.

Table 1 Protocol-Required Safety Laboratory Assessments

All study-required laboratory assessments will be performed by a central laboratory, with the exception of the serum and urine pregnancy tests, as well as the dipstick test for urinalysis. Instruction manuals and supply kits will be provided for all central laboratory assessments. Laboratory test variables measured will include:

Laboratory Assessments		Parameters
Hematology	•	Leukocytes, erythrocytes, hemoglobin, hematocrit, platelets, differential count (absolute) (neutrophils, eosinophils, basophils, monocytes and lymphocytes)
Clinical Chemistry	•	Sodium, potassium, chloride, bicarbonate, glucose (non-fasting) urea (BUN), creatinine, creatine phosphokinase (CPK), total protein, albumin, phosphate, calcium, magnesium, total bilirubin, alkaline phosphatase (ALP), alanine transaminase (ALT), aspartate aminotransferase (AST), gamma-glutamyl transferase (γ-GT), lactate dehydrogenase (LDH), HbA1c and GLDH (this last parameter will be optional; to be tested if the participant has elevated liver enzyme levels).
Coagulation	•	Prothrombin time (INR), activated partial thromboplastin time (aPTT).

Laboratory Assessments		Parameters	
Viral Serology	•	HIV (specific tests HIV-1 antibody, HIV-1/2 antibody, HIV-2 antibody), hepatitis B surface antigen (HBsAg), hepatitis C virus (HCV) antibody.	

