Lipids	•	Total cholesterol, LDL cholesterol, HDL cholesterol, triglycerides.	
Thyroid Hormones	•	Thyroxine (Free T4), thyroid stimulating-hormone (TSH)	
Hormone	•	Estradiol, follicle-stimulating hormone (FSH)	
a tubal occlusion/ligation) will have screening. At specified subsequen used; tests results will be evaluate		All women of childbearing potential (including those who have had a tubal occlusion/ligation) will have a blood pregnancy test at screening. At specified subsequent visits, urine sample will be used; tests results will be evaluated by the site's local laboratory. In case of a positive result on urine test, a confirmation with blood test has to be obtained.	
	•	Serum human chorionic gonadotropin (hCG) pregnancy test (as needed for women of childbearing potential).	
Urinalysis	•	Dipstick: pH, glucose, protein, blood, will be performed at the study center (or directly at the participant's home in case of an unscheduled home visit, see Section 8.11.4).	
		If there is a clinically significant positive result, urine will be sent to the central laboratory for repeat urinalysis and reflex microscopy and culture, as needed. As per operator judgement, a second dipstick testing can be conducted beforehand for confirmation of the positive result. If there is an explanation for the positive dipstick results (e.g., menses), it should be recorded and there is no need to perform microscopy and culture.	
	•	Microscopic examination (sediment, RBCs, WBCs, casts, crystals, epithelial cells, bacteria), if blood or protein is abnormal.	
Other Tests	•	Urine alcohol and drug screen (to include the following: amphetamines, barbiturates, cocaine, opiates, cannabinoids and benzodiazepines).	
	•	SARS-CoV-2 could be tested through serology and/or respiratory swab at the discretion of the Investigator and Sponsor at screening and/or at any time during the study.	

The results of each test must be entered into the eCRF if they are not uploaded to the database by the central laboratory.

Investigators must document their review of each laboratory safety report.

Based on continuous analysis of the data in this study, the Sponsor may decide at any time to stop the collection of any sample type not considered to be critical for safety if the data from the samples collected does not produce useful information.

Additional Statistical Considerations for Clinical Laboratory Data

Standard Reference Ranges and Transformation of Data

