1.1 OBJECTIVES AND ENDPOINTS

Table 1 Primary and Secondary Objectives

Primary Objective	Endpoint
To evaluate the efficacy of 12-week treatment with alogabat compared with placebo in treating social communication deficits in participants with Autism Spectrum Disorder (ASD)	 Change from baseline to Week 12 in the Adaptive Behavior Composite score of the Vineland[™] Adaptive Behavior Scales, Third Edition (Vineland[™]-3)
Secondary Objectives	Endpoints
To evaluate the safety and tolerability of a 12-week treatment with alogabat in 15-to 45-year-old participants with ASD	 Incidence and severity of adverse events (AEs) and serious adverse events (SAEs)

	Incidence of treatment discontinuations due to AEs Change from baseline over time and
	 Change from baseline over time and incidence of clinically relevant abnormalities in vital signs including orthostatic changes, electrocardiogram (ECG) parameters and safety laboratory values including the incidence of marked laboratory abnormalities
	 Change from baseline over time in suicide risk (using the Columbia-Suicide-Severity Rating Scale [C-SSRS])
	 Incidence of daytime sleepiness assessed with the Karolinska Sleepiness Scale (KSS), the Epworth Sleepiness Scale (ESS) or the ESS for children and adolescents (ESS- CHAD), and the Sudden Onset of Sleep Questionnaire
To evaluate the efficacy of a 12-week treatment with alogabat compared with placebo on restricted and repetitive behaviors (RRBs)	Change from baseline to Week 12 in behavior/symptoms as measured by all domains of the Repetitive Behavior Scale-Revised (RBS-R) scale
To evaluate the efficacy of a 12-week treatment with alogabat compared with placebo on social behaviors	Change from baseline to Week 12 on the Vineland-3 Socialization domain
To evaluate the efficacy of a 12-week treatment with alogabat compared with placebo on communication skills	Change from baseline to Week 12 on the Vineland-3 Communication domain

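### The open-ended Day 84 window in SAP Table 4 lets off-drug follow-up safety values be tabulated as Day 84

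*SAP*

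**What the plan says.** SAP Section 4.1, Table 4, assigns each assessment to an analysis day by study-day window. In every row the last column is Day 84, defined as study day 71 or later. No column follows it. For several values in one window the rule is: "If more than one assessment is in the same time window, the assessment that is closest to the planned study day will be selected". Listings keep all values.

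Protocol version 5, Section 1.3, Table 1, places the Week 12 visit at Day 84 ± 7 days. Follow-up visits come 14 and 42 days after it, each ± 7 days. Vital signs, CGI and the neurocognitive battery are collected at both. ECG, hematology, chemistry, coagulation and urinalysis are collected at the first. Protocol Section 8.11.3 has completers "return to the clinic approximately 2 weeks and 6 weeks after the last dose of study treatment for safety follow-up visits". Under Section 7.1, participants who stop treatment early "will be asked to return to the clinic for a study completion/early termination visit and may undergo follow-up assessments".

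Footnote 28 to protocol Table 1 reads: "TSH, free T4, and HbA1c will be assessed at screening, Week 6, and at the 2-week follow-up". Appendix 4 puts HbA1c in the Clinical Chemistry list ("lactate dehydrogenase (LDH), HbA1c and GLDH") but gives thyroid hormones a separate entry.

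The affected data belong to a secondary endpoint in SAP Section 1.1: "Change from baseline over time and incidence of clinically relevant abnormalities in vital signs including orthostatic changes, electrocardiogram (ECG) parameters and safety laboratory values". The SAP's one off-drug exclusion for clinical scales (Section 3) applies to efficacy analyses only.

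**The concern.** The Day 84 row is the end-of-treatment row of the by-visit safety tables and mean plots. A window with no upper limit also admits visits held after dosing has ended. Off-drug values can enter by three routes:

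1. **Missing Week 12 value.** The follow-up value is the only one in the window and is tabulated as Day 84.
2. **Early Week 12 visit with an early 2-week follow-up.** The follow-up can lie closer to Day 84 than the real Week 12 value and replace it. At equal distance the SAP gives no answer.
3. **Tests with no Week 12 draw.** Under footnote 28 the only scheduled HbA1c value from Day 71 on is the off-drug one.

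An on-drug effect could then be diluted, or a change after withdrawal could appear as an on-treatment change, with no flag in the table. Follow-up values not selected for Day 84 have no by-visit row. They remain in listings and may enter the abnormality tables, which are not titled by visit.

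**Working it through.** The plan states no figure on this point to reproduce. The check applies the Table 4 rule to every visit day that protocol version 5 allows, with one date per visit.

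**Inputs**
- Week 12 day w = 77 to 91 (84 ± 7).
- 2-week follow-up gap g = 7 to 21 days (14 ± 7); 6-week gap g = 35 to 49 days (42 ± 7).
- Day 84 window: study day ≥ 71; the value closest to Day 84 is selected (SAP Table 4).
- Half-life below about 20 hours (Protocol Section 8.3.7.1).
- Planned 20% without evaluable data (SAP Section 2.2).

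**Do follow-up visits fall in the window?** The follow-up day is w + g.
- 2-week visit: 77 + 7 = 84 to 91 + 21 = 112.
- 6-week visit: 77 + 35 = 112 to 91 + 49 = 140.

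All are ≥ 71, so when the Week 12 value is missing the follow-up value becomes Day 84 in all 225 of the 15 × 15 day pairs.

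**When does the 2-week visit displace a real Week 12 value?** The condition is |w + g − 84| < |w − 84|. Since w + g ≥ 84, it can hold only for w < 84, where it becomes g < 2(84 − w).

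| Week 12 day | Condition | Gaps that displace | Pairs | Tie at g = 2(84 − w) |
|---|---|---|---|---|
| 77 | g < 14 | 7-13 | 7 | Day 91 |
| 78 | g < 12 | 7-11 | 5 | Day 90 |
| 79 | g < 10 | 7-9 | 3 | Day 89 |
| 80 | g < 8 | 7 | 1 | Day 88 |
| 81 or later | g < 6 or less | none | 0 | none |

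Total: 7 + 5 + 3 + 1 = 16 of 225 displacements and 4 ties. At the planned gap of 14 days there are no displacements and one tie (77/91). The 6-week visit gives 0 displacements and 0 ties. These are counts of allowed day pairs, not expected frequencies.

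**Is the participant off drug by then?** At a half-life of 20 hours, 7 days is 168/20 = 8.4 half-lives, leaving 2^(−8.4) = 0.30% of drug. Fourteen days is 336/20 = 16.8 half-lives. With a shorter half-life less remains. This concerns drug level only, not whether a marker has returned to baseline.

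**Early discontinuers.** Assume their follow-up is timed from the last dose, on day L.
- Nominal 2-week visit: L + 14 ≥ 71 gives L ≥ 57 (50 to 64 across ± 7 days).
- Nominal 6-week visit: L + 42 ≥ 71 gives L ≥ 29 (22 to 36).

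**Ceiling for the missing-value route.** 20% × 105 = 21 participants, or 7 per arm; 7/35 = 20%. The range is 0 to 7 of 35.

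**Would an upper day limit alone be enough?** No. With a cap at Day 91, 98 or 105 the 16 displacements and 4 ties remain. A follow-up value would still fall in the window, and so fill an empty Day 84 cell, in 36, 120 or 197 of the 225 pairs.

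**The case against.** **The SAP may serve a later protocol version.** Table 4 has a Day 63 visit for adolescents that version 5 lacks, so footnote 28 and the follow-up schedule may have changed. This stands as a limit: the visit-based results hold under version 5. The unbounded window is in the SAP itself.

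**The closest-day rule already protects Week 12 values.** Largely true. Displacement needs Week 12 on Days 77-80 and a gap of 13 days or less. The rule does nothing for a missing Week 12 value or for a test with no Week 12 draw.

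**The 20% figure is a Vineland-3 planning assumption, not a rate of missing safety visits.** Correct. A participant can lack an evaluable Vineland-3 score and still have Week 12 laboratory values, and discontinuers need not attend follow-up. The figure serves only as an assumed ceiling.

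**TSH and free T4 may not belong to the chemistry row.** This is open. Footnotes 27 and 28 sit on the Blood Chemistry row of the protocol schedule, but Appendix 4 lists thyroid hormones separately. If they are outside that row, Table 4 gives them no window at all.

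**The consequence is small.** The safety summaries are descriptive, no formal testing is planned, and listings keep every value. The primary endpoint, RBS-R and CRRI are not collected at follow-up. CGI-I analyses are worded as at or up to 12 weeks of treatment and are partly covered by the missed-dose exclusion. All of this limits the weight of the point, but none of it corrects the by-visit safety tables and plots.

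**Conclusion.** The concern holds. Followed exactly, Table 4 can label off-drug follow-up values as Day 84 in the summaries of a named secondary safety endpoint. For HbA1c under footnote 28 it does so for the only scheduled value from Day 71 on. The extent of the missing-value route is unknown in advance. Displacement of a real Week 12 value is an edge case.

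The conclusion rests on the version 5 visit schedule. The HbA1c result also needs footnote 28 to be still in force, and the discontinuer thresholds assume timing from last dose. This should be corrected before the safety tables are produced; it does not threaten the primary analysis.

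**What to change.** - Add 2-week and 6-week follow-up windows to Table 4 for measures collected then, counted from the Week 12 visit, or from the last dose if there was none.
- State that nominal follow-up visits are never assigned to Day 84.
- For Day 84, select the nominal Week 12 visit first, use closeness to Day 84 only as a secondary rule, and name a tie-break, for example the earlier record.
- State which Table 4 row covers TSH and free T4. If footnote 28 still applies, report HbA1c, TSH and free T4 under the 2-week follow-up.
- Leave the Vineland-3, RBS-R and CRRI row unchanged.

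Early-termination and unscheduled records taken after stopping drug could still reach Day 84 through the secondary rule, so the SAP should also say how they are handled.

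The cost is a few Table 4 columns and by-visit table rows, with no new data. The safety tables would have slightly fewer Day 84 values, and HbA1c would have no scheduled Day 84 value (nor would TSH and free T4, if they belong to the chemistry row).

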Week	Screening	Pre-Baseline	Baseline	Week 1	Week 1	Week 2	Week 6	Week 12	Follow-up (2 Weeks)	Follow-up (6 Weeks)	Early Termination	
Day	D-42 to D-15	Day -14	(Days -3 to -1)	Day 1	Day 7	Day 14	Day 42	Day 84	Week 12 visit + 14 days	Week 12 visit + 42 days		
Visit Window ¹		+/- 3 days			+/- 3 days	+/- 7 days	+/- 7 days	+/- 7 days	+/- 7 days	+/- 7 days		
Assessments	Site Visit	Site Visit	Site Visit	Site Visit	Phone call ²⁰	Site Visit	Site Visit	Site Visit	Site Visit	Site Visit	Site Visit	
KSS ²⁵				x		x	x	x				
ESS or ESS-CHAD 22				x		x	x	x			x	
Sudden Onset of Sleep Questionnaire				x ²	x	x	x	x			x	
PROMIS Sleep Disturbance Short Form 22			х					х				
PROMIS Sleep-Related Impairment Short Form 22			x					x				
PD Biomarker (qEEG, SPV)		x 12		x ^{12,14}		x ¹²		x 12				
Response BM (Eyetracking)		x ¹³						x 13				
Response BM (EEG Tasks)		x ¹³						x ¹³				
Serology ²⁶	x											
Hematology	x		х			х	х	х	x		х	
Blood Chemistry	x ^{27, 28}		x			х	x ²⁸	х	x ²⁸		x	
Coagulation	x		x					x	x		x	
Urinalysis	x		х			х	х	x	x		х	
Drug of abuse/Alcohol test	x		х					x				
Hair sample collection 33			x				x	x		x		
C-SSRS 31	х		x			х	х	х	x	x	х	
Randomization				x								
Dispensing of study medication				x			x					
Return of study medication							x	x			x	
Administration of study medication at clinic ¹⁰												
Digital biomarkers					x ¹⁵						x ¹⁵	
PK Sample				x ^{11,17}		x ^{11,17}	x ^{9,17}	x ^{9,17}			x ¹⁷	
Blood sample for Clinical Genotyping									x ¹⁶			
Entry and exit questions ²²			x					x			х	
RBR - Optional Whole Blood Sample				x ¹⁹				x ¹⁹			x ¹⁹	
Safety serum sample		x ²¹										
Adverse Events							х					

Table 1 Schedule of Activities - 12-Week, Double-Blind, Placebo-Controlled Period and Follow-Up (cont.)

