8.11.2 Assessments during Treatment

Under no circumstances will participants who enroll in this study and have completed treatment as specified be permitted to be allocated a new randomization number and reenroll in the study.

All assessments must be performed as per SoA (see Section 1.3). The recommended order of assessments to be performed at the clinic will be defined in a separate document. The order of assessments may be adapted to allow efficient administration of all assessments at the site with the exception of assessments that have to be done at a specific time before or after taking the study drug as per SoA (see Section 1.3). The order of assessments that have to be taken at home is predefined on the electronic device for each participant (see Section 8.7.1.1). The site will contact the participant or support person over the phone to assess for any clinically significant symptoms and/or new medication, to ensure compliance to the study drug and digital biomarker assessments as well as to administer questionnaires/scales/tests when appropriate as per SoA (see Section 1.3).

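### Week 2 Sudden Onset of Sleep questionnaires done on Days 7-10 are on time under the protocol but fall in the SAP's Day 7 window, where one of two valid records can be left out of the summary table

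*SAP*

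**What the plan says.** In the protocol's Schedule of Activities (Section 1.3, Table 1), the row "Sudden Onset of Sleep Questionnaire" is marked at both the Day 7 phone call and the Week 2 site visit, among other contacts. The planned days run "Day 7 Day 14 Day 42", with tolerances of +/- "3 days +/- 7 days +/- 7 days". Section 8.11.2 confirms that site calls can be used "as well as to administer questionnaires/scales/tests when appropriate as per SoA".

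SAP Section 4.1 works by study day: "Assessments will be assigned to analysis study days according to visit windows defined below". In Table 4 the row for this questionnaire gives Days 2-10 for the Day 7 column and Days 11-28 for the Day 14 column. The rule for duplicates, which applies to the summary tables, is: "If more than one assessment is in the same time window, the assessment that is closest to the planned study day will be selected". The same section says that listings show multiple records. It gives no exception by nominal visit and no rule for ties.

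The planned-day row of Table 4 reads "1 (a) 1 1 14 42 63 84", so the entry under Day 7 is 1 in the text as extracted.

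SAP Table 1 lists incidence of daytime sleepiness, measured by KSS, ESS or ESS-CHAD and this questionnaire, as a secondary safety endpoint. SAP Table 10 promises summary tables and listings for it. Appendix 1 names one summary table, t_sudden.

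**The concern.** Two compliant contacts can land in one analysis window. When they do, a rule that keeps only the record nearest a planned day decides which answer is tabulated, whatever the answer was. The questionnaire asks whether episodes occurred and how often, so the call and the visit are separate reports and one cannot stand in for the other. For an endpoint defined as incidence, a positive answer on the unselected record can be missing from t_sudden.

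The filing is also uneven within one visit. For a Week 2 visit on Day 8, Table 4 puts KSS and ESS or ESS-CHAD under Day 14 (their window is Days 2-28) but this questionnaire under Day 7. Components of one endpoint, collected at the same visit, would be shown at different timepoints.

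**Working it through.** **Inputs.** Call: Day 7 +/- 3. Week 2 visit: Day 14 +/- 7 (Protocol Tables 1 and 2). SAP windows for this questionnaire: Days 2-10 and 11-28 (SAP Table 4).

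**1. Reproduce the SAP cuts.** They are midpoints of planned days: (7 + 14)/2 = 10.5 gives the 10/11 cut, and (14 + 42)/2 = 28 gives the upper limit. A planned day of 1 would give (1 + 14)/2 = 7.5, which does not match. The entry of 1 under Day 7 is therefore probably a slip or an extraction artefact, with 7 intended.

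**2. Protocol windows.** Call: 7 - 3 = 4 to 7 + 3 = 10. Week 2 visit: 14 - 7 = 7 to 14 + 7 = 21, which is 15 days.

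**3. Overlap.** Days 7-21 and Days 2-10 share Days 7, 8, 9 and 10, which is 4 of the 15 permitted Week 2 days (4/15 = 27%). Days 11-21 are filed correctly. Every in-window call (Days 4-10) lies in the Day 7 window, so a Week 2 visit on Days 7-10 always shares that window with an on-time call. The Week 6 (35-49) and Week 12 (77-91) visits fit inside their SAP windows.

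**4. Collisions.** Count day pairs with the call before the visit, for calls on Days 4, 5, 6, 7, 8, 9 and 10:
- all pairs: 15 + 15 + 15 + 14 + 13 + 12 + 11 = 95
- pairs with the visit on Days 7-10: 4 + 4 + 4 + 3 + 2 + 1 + 0 = 18

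So 18/95 = 19% of permitted day pairs collide. This is a count of possibilities, not a forecast of participants.

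**5. Which record is kept in the 18 collisions.**

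| Planned day used | Call kept | Week 2 kept | Tie |
|---|---|---|---|
| 1 (as read) | 18 | 0 | 0 |
| 7 (probably intended) | 9 | 6 | 3 |

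In each collision Day 14 is empty for that participant unless another record falls in Days 11-28.

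**6. Would a different cut help?** Suppose the Day 7 window ends on Day k, with k from 6 to 10. Misfiled Week 2 days number k - 6 and misfiled call days number 10 - k, so the total is always 4. The cause is the overlap of the protocol's own windows on Days 7-10. Assignment by nominal contact misfiles none.

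**7. How many participants?** The documents give no distribution of visit days. As assumptions only, the share of Week 2 visits on Days 7-10 would be 27% if they were spread evenly over the 15 days. If they centred on Day 14 it would be 12% with SD 3, 4% with SD 2 and 1% with SD 1.5. The range is too wide to support a participant count.

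**The case against.** The strongest reply is that little is lost. Listings keep duplicates, and SAP Table 10 promises listings for this questionnaire. Sudden onset of sleep is itself a non-serious adverse event of special interest (Protocol Section 8.3.6), to be reported within 24 hours, and the SAP plans a table and a listing of such events with no one-record rule. The same filing rule applies in every arm of a blinded study with no formal hypothesis testing, so no directional bias is shown. A Day 8 record does reflect about one week of exposure, and the 10/11 cut is an ordinary midpoint, no worse than any other cut from Day 6 to Day 10.

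All of this stands, and it limits the size of the point. One qualification is that the readable part of Appendix 1 shows t_sudden but no listing for this questionnaire; that list may be incomplete as extracted. The reply does not explain why an incidence summary should omit a valid answer, and it supplies no tie-break.

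Three stronger readings are tempting but not supported:
- **All on-time Week 2 questionnaires are misfiled.** Only those on Days 7-10 are; the nominal Day 14 is filed correctly.
- **Events disappear from the safety report.** Only a questionnaire answer can leave one table.
- **The Day 14 denominator shrinks.** Section 4.1 bases percentages on participants exposed, so this is not established. The title of t_sudden does not say that it is laid out by visit.

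**Conclusion.** The inconsistency is real and minor. A compliant Week 2 questionnaire on Days 7-10 is filed as Day 7 and, when the call was also on time, one of two valid records is left out of the summary table. This can happen on 4 of 15 permitted Week 2 days and in 18 of 95 permitted day pairs. The number of participants affected cannot be known from the documents.

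The conclusion assumes that the Protocol Version 5 windows still apply, which the sponsor should confirm because SAP Table 4 carries a Day 63 column for adolescents that the Version 5 schedule lacks. It also assumes that the call precedes the visit; allowing both on the same day changes the count to 22 of 99. Which record is kept depends on whether the planned day is 1 or 7, but the collision itself does not. No efficacy analysis is affected.

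**What to change.** 1. Summarise the incidence endpoint for this questionnaire as any positive answer on any post-baseline questionnaire, scheduled or not, without closest-day selection. This corrects the omission however by-visit records are assigned.
2. For by-visit displays of this questionnaire, assign records by nominal contact (Day 7 call or Week 2 visit) rather than by study day.
3. Check the planned study day under Day 7 in Table 4, and correct it if 7 was meant.

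The cost is a few SAP sentences and a small amount of programming, provided that the contact type is recorded with each questionnaire; the documents suggest this but do not state it. The downside is that an early Week 2 record would be shown as Week 2 although it reflects only about one week of exposure.
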